5. REPORTING OF ADVERSE EVENTS

5.1 ASSESSMENT OF SAFETY

Specification of Safety Variables

Safety assessments will consist of monitoring and reporting adverse events (AEs) and serious adverse events (SAEs) per protocol. This includes all events of death, and any study specific issue of concern.

Adverse Events

An AE is any unfavorable and unintended sign (including an abnormal laboratory finding), symptom, or disease temporally associated with the use of an investigational medicinal product (IMP) or other protocol-imposed intervention, regardless of attribution.

This includes the following:

• AEs not previously observed in the subject that emerge during the protocolspecified AE reporting period, including signs or symptoms associated with Multiple Sclerosis that were not present prior to the AE reporting period.

- Complications that occur as a result of protocol-mandated interventions (e.g., invasive procedures such as cardiac catheterizations).
- If applicable, AEs that occur prior to assignment of study treatment associated with medication washout, no treatment run-in, or other protocol-mandated intervention.
- Preexisting medical conditions (other than the condition being studied) judged by the investigator to have worsened in severity or frequency or changed in character during the protocol-specified AE reporting period.

Serious Adverse Events

An AE should be classified as an SAE if the following criteria are met:

- It results in death (i.e., the AE actually causes or leads to death).
- It is life threatening (i.e., the AE, in the view of the investigator, places the subject at immediate risk of death. It does not include an AE that, had it occurred in a more severe form, might have caused death.).
- It requires or prolongs inpatient hospitalization.
- It results in persistent or significant disability/incapacity (i.e., the AE results in substantial disruption of the subject's ability to conduct normal life functions).

• It results in a congenital anomaly/birth defect in a neonate/infant born to a mother exposed to the IMP.

• It is considered a significant medical event by the investigator based on medical judgment (e.g., may jeopardize the subject or may require medical/surgical intervention to prevent one of the outcomes listed above).

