5.3 PROCEDURES FOR ELICITING, RECORDING, AND REPORTING ADVERSE EVENTS

Eliciting Adverse Events

A consistent methodology for eliciting AEs at all subject evaluation time points should be adopted. Examples of non-directive questions include:

- "How have you felt since your last clinical visit?"
- "Have you had any new or changed health problems since you were last here?"

Specific Instructions for Recording Adverse Events

Investigators should use correct medical terminology/concepts when reporting AEs or SAEs. Avoid colloquialisms and abbreviations.

a. Diagnosis vs. Signs and Symptoms

If known at the time of reporting, a diagnosis should be reported rather than individual signs and symptoms (e.g., record only liver failure or hepatitis rather than jaundice, asterixis, and elevated transaminases). However, if a constellation of signs and/or symptoms cannot be medically characterized as a single diagnosis or syndrome at the time of reporting, it is acceptable to report the information that is currently available. If a diagnosis is subsequently established, it should be reported as follow-up information.

b. Deaths

All deaths that occur during the protocol-specified AE reporting period (see Section 5.1.2), regardless of attribution, will be reported to the appropriate parties. When recording a death, the event or condition that caused or contributed to the fatal outcome should be reported as the single medical concept. If the cause of death is unknown and cannot be ascertained at the time of reporting, report "Unexplained Death".

c. Preexisting Medical Conditions

A preexisting medical condition is one that is present at the start of the study. Such conditions should be reported as medical and surgical history. A preexisting medical condition should be re-assessed throughout the trial and reported as an AE or SAE only if the frequency, severity, or character of the condition worsens during the study. When reporting such events, it is important to convey the concept that the preexisting condition has changed by including applicable descriptors (e.g., "more frequent headaches").

d. Hospitalizations for Medical or Surgical Procedures

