Any AE that results in hospitalization or prolonged hospitalization should be documented and reported as an SAE. If a subject is hospitalized to undergo a medical or surgical procedure as a result of an AE, the event responsible for the procedure, not the procedure itself, should be reported as the SAE. For example, if a subject is hospitalized to undergo coronary bypass surgery, record the heart condition that necessitated the bypass as the SAE.

Hospitalizations for the following reasons do not require reporting:

- Hospitalization or prolonged hospitalization for diagnostic or elective surgical procedures for preexisting conditions
- Hospitalization or prolonged hospitalization required to allow efficacy measurement for the study or
- Hospitalization or prolonged hospitalization for scheduled therapy of the target disease of the study.

e. Assessment of Severity of Adverse Events

The adverse event severity grading scale for the NCI CTCAE (v5 .0 Update current versions) will be used for assessing adverse event severity. Below Table should be used for assessing severity for adverse events that are not specifically listed in the NCI CTCAE.

Adverse Event Severity Grading Scale for Events Not Specifically Listed in NCI CTCAE

Grade	Severity
1	Mild; asymptomatic or mild symptoms; clinical or diagnostic observations only; or intervention not indicated
2	Moderate; minimal, local, or non-invasive intervention indicated; or limiting age-appropriate instrumental activities of daily living ^a
3	Severe or medically significant, but not immediately life-threatening; hospitalization or prolongation of hospitalization indicated; disabling; or limiting self-care activities of daily living ^{b,c}
4	Life-threatening consequences or urgent intervention indicated d
5	Death related to adverse event ^d

NCI CTCAE = National Cancer Institute Common Terminology Criteria for Adverse Events.

Note: Based on the most recent version of NCI CTCAE (v5.0), which can be found at: http://ctep.cancer.gov/protocolDevelopment/electronic_applications/ctc.htm

- a. Instrumental activities of daily living refer to preparing meals, shopping for groceries or clothes, using the telephone, managing money, etc.
- b. Examples of self-care activities of daily living include bathing, dressing and undressing, feeding oneself, using the toilet, and taking medications, as performed by patients who are not bedridden.

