APPENDIX A Schedule of Assessments

	Screening/ BL ^{1,2}	M3	M6 ³	M9	M12 ³	M15	M18 ³	M21	M24 ³
Informed Consent	Х								
Review of Medical History	Х								
Review of inclusion/exclusion	Х								
Concomitant Medications	Х	Х	Х	Х	Х	Х	Х	Х	Х
Demographics	Х								
Patient Questionnnaires (UEFI, SDMT, FSS, MUSIQOL)	X	Х	Х	Х	Х	Х	Х	Х	Х
Physical Exam (and EDSS)	Х		Х		Х		Х		Х
Vital Signs	Х	X ⁴	Х	X4	Х	X4	Х	X4	Х
Interval History	Х	Х	Х	Х	Х	Х	Х	Х	Х
Review AEs	Х	Х	Х	Х	Х	Х	Х	Х	Х
Measurement of UE function (TEMPA, 9HPT, Jamar dynamometer)	Х		X		X		X		Х
Relapse Assessment ⁵	Х	Х	X	Х	Х	Х	X	Х	Х

1. The baseline visit will occur within 4 weeks of the screening visit.

2. Acceptable windows for all visits are +/- 14 days. In rare cases where the first infusion is greater than 2 months from the baseline visit, the month 3 visit and subsequent visits will be calculated based on the initial infusion date.

3. Semiannual visits will occur prior to the next scheduled Ocrevus™ infusion

4. Vitals signs will be collected for subjects who conduct the quarterly visit at clinic. Vital signs will not be collected at quarterly visits conducted via phone.

5. If relapse is suspected, this will be captured as an AE and treated at the discretion of the investigator. Documentation will include any suspicion for PML

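### The first reporting exemption in Section 5.3d is not limited to preexisting conditions that stayed stable, so an admission for a worsened one could miss classification as serious

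*Combined protocol and SAP*

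**What the plan says.** Four pieces of the safety text bear on the same admission.

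- **Section 5.1** counts a preexisting condition that the investigator judges to have worsened as an AE, but excludes the disease under study from that clause. One of its criteria for a serious event is "It requires or prolongs inpatient hospitalization".
- **Section 5.3, item c** says a preexisting condition is to be "reported as an AE or SAE only if the frequency, severity, or character of the condition worsens during the study".
- **Section 5.3, item d, opening** states the general rule: "Any AE that results in hospitalization or prolonged hospitalization should be documented and reported as an SAE". The second sentence covers admissions for a procedure that an AE has made necessary: "the event responsible for the procedure, not the procedure itself, should be reported as the SAE". The example is coronary bypass, where the investigator is told to "record the heart condition that necessitated the bypass as the SAE".
- **Section 5.3, item d, list** follows directly. It is introduced by "Hospitalizations for the following reasons do not require reporting", and its first entry is "Hospitalization or prolonged hospitalization for diagnostic or elective surgical procedures for preexisting conditions".

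**The concern.** The exemption carries no condition about the course of the illness. It applies to a preexisting condition whether it stayed the same or deteriorated after enrolment, and it covers prolonged stays as well as new admissions. Because the list comes straight after the general rule, an investigator can reasonably take it as the set of exceptions to that rule. Nothing in 5.3 says which prevails when both apply.

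What is at stake is seriousness. It decides which reporting route and timeline an event follows, and it decides whether the event appears among the SAEs when the study is written up. Two assessors, or one assessor on two occasions, could classify the same admission differently and each point to a sentence in item d.

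**Working it through.** The plan states no figure on this point, so the check sets the passages side by side and goes through the possible cases.

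**Step 1. Where the rules agree and where they part.**

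1. *Preexisting condition unchanged; admission for a diagnostic or elective surgical procedure.* It is not an AE under 5.1 or item c, so the general rule in item d is not triggered. The exemption applies. No conflict.
2. *Preexisting condition worsened; admission for something other than a diagnostic or elective surgical procedure.* It is an AE under 5.1 and item c, and serious because of the admission. The first exemption does not reach it. No conflict.
3. *Event not present at study start; admission for any procedure.* It is an AE and serious because of the admission. The exemption concerns preexisting conditions only. No conflict.
4. *Preexisting non-MS condition worsened; admission, or a longer stay, for a diagnostic or elective surgical procedure.* It is an AE under 5.1 and item c, and an SAE under 5.1 and the first two sentences of item d. It also fits the words of the first exemption. **Conflict.**

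The passages disagree only in case 4.

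**Step 2. Whether the bypass example settles case 4.** It does not. The example does not say whether the heart condition was present at study start or whether the operation was elective, so it cannot show which rule takes priority.

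**Step 3. What depends on the classification.**

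- Section 5.3, item j: an SAE related to the product goes to the manufacturer within 15 calendar days. An unrelated SAE goes at least annually through the AE master log. An event not classed as serious falls outside both.
- Section 5.6: the 15-calendar-day written report to the FDA is required for events that are serious, unexpected and reasonably or possibly related. The 7-day report concerns fatal or life-threatening events. Those are serious in their own right, so the exemption does not put that report at risk.
- Section 6.4: prompt IRB notification applies to reactions that are both serious and unexpected.

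**Step 4. Whether another step would catch the omission.** Section 6.5 gives study monitoring as not applicable. The case transmission verification in item h of 5.3 checks that reports already sent have arrived. Neither is designed to find an admission that was never classed as serious.

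**Step 5. What does not depend on it.** The worsened condition is still an AE under 5.1 and item c, and item j requires all AEs to be reported. It would still enter the descriptive AE summary in 4.9.4. The termination ground in 4.8 refers to the incidence or severity of AEs and sets no SAE threshold. The TEMPA analyses in 4.9.3 do not use AE data.

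**Step 6. Scale.** Section 4.9.6 plans for 30 patients. If the summary separates serious events, one reclassified event in a patient with no other SAE moves the proportion of patients with an SAE by 1/30 = 3.3 percentage points.

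**The case against.** The best answer is that item d can be read as a whole. Item c makes a preexisting condition reportable only when it worsens. The first two sentences of item d then make an AE-driven admission serious. The exemption can be confined to what is left, namely unchanged conditions, which are not AEs. On that reading every sentence has work to do and nothing conflicts.

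That reading is sensible and probably intended. It still requires the reader to supply a limit that the exemption does not state, and the position of the list after the rule points the other way. So the ambiguity stands, although it is one of wording.

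Seriousness also has other routes. Section 5.1 includes persistent disability, threat to life and the investigator's judgement of medical significance, and 5.3 item e makes grade 4 and 5 events serious. This narrows the gap. It does not close it for an event whose only serious feature is the admission.

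A reader might go further and infer that the exemption reaches every patient, because all have MS at entry, so that even a work-up for suspected relapse or PML would escape. The documents do not support this. Section 5.1 excludes the disease under study from its worsening clause and separately counts new MS signs or symptoms as AEs. Footnote 5 of Appendix A says "If relapse is suspected, this will be captured as an AE and treated at the discretion of the investigator" and asks that any suspicion of PML be documented. PML would be a new diagnosis, not a condition present at study start.

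**Conclusion.** The conflict is real but narrow. Read literally, the first exemption in item d contradicts 5.1, item c and the opening of item d for one kind of event: a preexisting condition other than MS that worsens on study and leads to admission, or a longer stay, for a diagnostic or elective surgical procedure. Such an event could be left unclassified as serious and so miss the SAE routes in 5.3 item j, 5.6 and 6.4.

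The conclusion assumes that an investigator applies the exemption as written and that no other seriousness criterion is met. Its frequency cannot be given, because the documents state no admission rate for this population.

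Two other stronger inferences should be resisted. The event would not vanish from the record, since it stays reportable as an AE. Nor can there be differences between sites, because Section 4.0 places the study at a single centre. Efficacy results and sample size are unaffected.

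**What to change.** Reconcile item d of 5.3 with 5.1 and with item c in two short edits:

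1. At the end of the first exemption, add the limit: *that have not worsened since baseline (see 5.3c)*.
2. After the list, state that an admission resulting from an event recorded as an AE is reported as an SAE under the opening rule of item d.

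The first edit resolves the conflict. The second settles which rule takes priority. No further restriction, for example on when the procedure was planned, is needed for this purpose.

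The cost is one or two sentences of text and perhaps a few additional SAE forms. No assessment, visit or analysis changes.

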5.4 MedWatch 3500A Reporting Guidelines

In addition to completing appropriate patient demographic and suspect medication information (Section C & D), the report should include the following information within the Event Description (section B.5) of the MedWatch 3500A form:

- Protocol description (and number, if assigned)
- Description of event, severity, treatment, and outcome if known
- Supportive laboratory results and diagnostics (Section B.6)
- Investigator's assessment of the relationship of the AE to each investigational product and suspect medication

Follow-up Information

Additional information may be added to a previously submitted report by any of the following methods:

- Adding to the original MedWatch 3500A report and submitting it as follow-up
- Adding supplemental summary information and submitting it as follow-up with the original MedWatch 3500A form
- Summarizing new information and faxing it with a cover letter including patient identifiers (i.e. D.O.B. initial, patient number), protocol description and number, if assigned, brief AE description, and notation that additional or follow-up information is being submitted (The patient identifiers are important so that the new information is added to the correct initial report).

MedWatch 3500A (Mandatory Reporting) form is available at https://www.fda.gov/media/69876/download

5.5 Reporting to Regulatory Authorities, Ethics Committees and Investigators

The Sponsor of the Study will be responsible for the expedited reporting of safety reports originating from the Study to the Regulatory Authorities (FDA) where it has filed a clinical trial approval, in compliance with local regulations.

Genentech will be responsible for the expedited reporting of safety reports originating from the Study to the EMA through Eudravigilance Clinical Trial Module (EVCTM). The

Sponsor will be responsible for the distribution of safety information to its own investigators, where relevant.

5.6 Additional Reporting Requirements for IND Holders

For Investigator-Initiated Studies, some additional reporting requirements for the FDA apply in accordance with the guidance set forth in 21 CFR § 600.80.

Events meeting the following criteria need to be submitted to the Food and Drug Administration (FDA) as expedited IND Safety Reports according to the following guidance and timelines:

7 Calendar Day Telephone or Fax Report:

The Investigator is required to notify the FDA of any fatal or life-threatening AE that is unexpected and assessed by the Investigator to be possibly related to the use of ocrelizumab. An unexpected AE is one that is not already described in the ocrelizumab IB. Such reports are to be telephoned or faxed to the FDA and Genentech/Roche within 7 calendar days of first learning of the event.

15 Calendar Day Written Report

The Investigator is also required to notify the FDA and all participating investigators, in a written IND Safety Report, of any serious, unexpected AE that is considered reasonably or possibly related to the use of ocrelizumab. An unexpected AE is one that is not already described in the ocrelizumab IB.

Written IND Safety reports should include an Analysis of Similar Events in accordance with regulation 21 CFR § 312.32. All safety reports previously filed by the investigator with the IND concerning similar events should be analyzed and the significance of the new report in light of the previous, similar reports commented on.

Written IND safety reports with Analysis of Similar Events are to be submitted to the FDA, Genentech/Roche, and all participating investigators within 15 calendar days of first learning of the event. The FDA prefers these reports on a MedWatch 3500 form, but alternative formats are acceptable (e.g., summary letter).

FDA fax number for IND Safety Reports:

Fax: [name]

All written IND Safety Reports submitted to the FDA by the Investigator must also be faxed to Genentech/Roche Drug Safety: [contact] or [contact]

And the sponsor will be responsible for the distribution of safety information to Site IRB:

University of South Florida IRB [name] [contact]

For questions related to safety reporting, please contact Genentech/Roche Drug Safety: [contact] [contact] or [contact]

AGGREGATE REPORTS

IND ANNUAL REPORTS

All IND annual reports submitted to the FDA by the Sponsor-Investigator should be copied to Genentech:

Copies of such reports should be emailed to Genentech at: [contact] and [contact]

Other Reports

The sponsor will forward a copy of the Final Study Report or publication to Genentech/Roche upon completion of the Study.

Study Close-Out

Any study report submitted to the FDA by the Sponsor-Investigator should be copied to Genentech. This includes all IND annual reports and the Clinical Study Report (final study report). Additionally, any literature articles that are a result of the study should be sent to Genentech. Copies of such reports should be mailed to the assigned Clinical Operations contact for the study:

[contact], to Genentech Drug Safety CTV oversight mail box at: [contact] and your Genentech MSL.

QUERIES

Queries related to the Study will be answered by University of South Florida. However, responses to all safety queries from regulatory authorities or for publications will be discussed and coordinated between the Parties. The Parties agree that Genentech/Roche shall have the final say and control over safety queries relating to the Product. University of South Florida agrees that it shall not answer such queries from regulatory authorities and other sources relating to the Product independently but shall redirect such queries to Genentech.

Both Parties will use all reasonable effort to ensure that deadlines for responses to urgent requests for information or review of data are met. The Parties will

clearly indicate on the request the reason for urgency and the date by which a response is required.

SAFETY CRISIS MANAGEMENT

In case of a safety crisis, e.g., where safety issues have a potential impact on the indication(s), on the conduct of the Study, may lead to labeling changes or regulatory actions that limit or restrict the way in which the Product is used, or where there is media involvement, the Party where the crisis originates will contact the other Party as soon as possible.

The Parties agree that Genentech/Roche shall have the final say and control over safety crisis management issues relating to the Product. University of South Florida agrees that it shall not answer such queries from media and other sources relating to the Product but shall redirect such queries to Genentech/Roche.

6. INVESTIGATOR REQUIREMENTS

6.1 STUDY INITIATION

Before the start of this study, the following documents must be on file with Genentech or a Genentech representative:

 Original U.S. FDA Form 1572 for each site (for all studies conducted under U.S. Investigational New Drug [IND] regulations), signed by the Principal Investigator

The names of any sub-investigators must appear on this form. Investigators must also complete all regulatory documentation as required by local and national regulations.

- Current curriculum vitae of the Principal Investigator
- Written documentation of IRB approval of protocol and informed consent document
- A copy of the IRB-approved informed consent document
- A signed Clinical Research Agreement

